4.5 Withdrawal of individual subjects

A subject will be withdrawn if ANY of the following criteria are met:

- The subject wishes to withdraw from further participation
- The subject is significantly noncompliant with the Protocol
- The subjects is discontinued due to safety reason; continuing in the study would be detrimental to the subject's safety in the opinion of the Investigator, such as
 - The subject experiences intolerable AEs or SAEs
 - The subject has clinically significant changes in safety parameters at any of the post-dose time points, as confirmed with a repeat assessment performed as soon as possible after the initial out-of-range result

In addition, a subject may be withdrawn at any time for any reason other than those listed here.

If a subject is discontinued prematurely from the study, the date the subject is withdrawn from the study and the reason for withdrawal will be recorded on the CRF.

In case of withdrawal of a subject, the Follow-up Visit assessments should be performed, as far as possible (Section 5.2.3).

Any withdrawal due to an AE or for any safety reason should always be considered serious.

Any unresolved AE or SAE will be followed up according to Section 8.9.

In the event that a subject elects not to return to the study center for the end of study visit, the Investigator must make every effort to contact the subject to review all AEs. In the event that a subject drops out of the study at any time, the reason for discontinuation must be fully documented in the source documents and the CRF. The study center personnel will document the AEs and any other assessments in the source documents and will make every effort to complete all required end of study assessments.

Subjects withdrawn for non-treatment-related reasons may be replaced at the discretion of the Sponsor and Investigator. Replacement subjects will receive the treatments intended for the withdrawn subject.

Criteria for amendment of dose in subjects with mild renal impairment (Group 1)

The subjects with mild renal impairment will be treated first. The second subject with mild renal impairment will not be treated until the completion of review for safety and PK profile in the first treated subject by the Sponsor and the Investigator. [REDACTED]

[REDACTED]

Procedure and criteria for starting treatment of subjects with moderate renal impairment (Group 2)

Three subjects with mild renal impairment will be treated, and then the investigator and the Sponsor will assess the safety and PK results in these three subjects until after the end of trial (Day 7). A safety and PK review will be performed by the investigator and the Sponsor including the Medical advisor. The safety report will be compiled by the investigator, and the PK report will be compiled by [REDACTED]. The Sponsor will calculate C_{max} and AUC for the three subjects, against predicted C_{max} and AUC. The investigator and the Sponsor will decide together, if there are no safety and PK concerns in all three subjects with mild renal impairment, subjects with moderate renal impairment may be included. Progression to treatment of subjects with moderate renal impairment will not occur until this safety and PK review has been performed and approval is recorded by the investigator and the Sponsor.

Detailed procedure is described in a separate document.

If any of the following criteria are fulfilled, progression to treatment of subjects with moderate renal impairment will be temporarily stopped.

- ≥ 2 subjects in the three subjects have severe or serious IMP-related AEs, or
- ≥ 2 subjects in the three subjects have ALT or AST $>3 \times$ ULN in conjunction with elevated total bilirubin $>2 \times$ ULN at any point after treatment, or
- ≥ 2 subjects in the three subjects have ALT or AST $>3 \times$ ULN with appearance of fatigue, nausea, vomiting, right upper quadrant pain or tenderness, fever, rash and/or eosinophilia ($>5\%$), or

- ≥ 2 subjects in the three subjects have creatinine $> 1.5 \times$ at baseline value

Criteria for amendment of dose in subjects with moderate renal impairment (Group 2)

The first subjects with moderate renal impairment will be assessed the safety and PK profile by the Investigator and the Sponsor. The second subject with moderate renal impairment will not be treated until the completion of review for safety and PK profile in the first treated subject by the Sponsor and the Investigator.

the dose may be changed.

If there are significant safety concerns, the study may be stopped.

4.6 Lifestyle restrictions

Subjects will be advised that they must adhere to the following restrictions:

4.6.1 Attendance

- Availability to attend visits according to the Protocol.
- Availability for overnight stays in the study center from Day -1 to Day 3.

4.6.2 Alcohol restrictions

- Subjects should refrain from consuming food or drink containing alcohol in the 24 hours before each visit and whilst confined to the study center.
- Subjects should avoid excessive consumption (> 16 g as pure alcohol per day) of food or drink containing alcohol at all other times from the Screening Visit until the Follow-up assessment.

4.6.3 Xanthines

- Subjects should refrain from consuming food or drink containing caffeine and methylxanthine (e.g., coffee, tea, cola, energy drinks or chocolates) in the study center from Day -1 to Day 3, and from an awakening of the day of the Screening or Follow-up Visits until end of each examination.
- Subjects should avoid excessive consumption (> 5 cups of coffee or equivalent per day) of food or drink containing caffeine and methylxanthine (e.g., coffee, tea, cola, energy drinks or chocolates) at all other times from the Screening Visit until the Follow-up assessment.

4.6.4 Smoking

No smoking or using tobacco- or nicotine-containing products (snuff, chewing tobacco, cigarettes, cigars, pipes, e-cigarettes or nicotine replacement products) in the study center from Day -1 to Day 3, and from an awakening of the day of the Screening or Follow-up Visits until end of each examination.

4.6.5 Contraception

Female subjects of child-bearing potential* must be willing and able to practice birth control for the duration of the study, from the Screening or at least 2 weeks before IMP administration (whichever is earlier) until 14 days after the last dose of IMP. Male subjects must be willing and able to practice birth control for the duration of the study, from the time of the first dose of IMP until 14 days after the last dose of IMP.

- **Female subjects** must be willing to use a highly effective method of birth control (*i.e.*, contraceptive measure with a failure rate of <1% per year), in conjunction with male barrier contraception (*i.e.*, male condom with spermicide). Highly effective methods of contraception include:
 - Placement of an intrauterine device.
 - Established use of oral hormonal methods of contraception associated with inhibition of ovulation.
 - Male sterilisation (with the appropriate post-vasectomy documentation of the absence of sperm in the ejaculate). (For female subjects on the study, the vasectomised male partner should be the sole partner for that subject.)
 - Bilateral tubal ligation.
- **Male subjects** with partners of child-bearing potential must use a barrier method of contraception (*i.e.*, male condom with spermicide) in addition to a second method of acceptable contraception used by their female partners. In addition to the list of highly effective contraception methods above, other acceptable methods of contraception include:
 - Diaphragm with spermicide.

Male subjects must not donate sperm for the duration of the study, from the time of the first dose of IMP until 14 days after the last dose of IMP.

*Note: Women are considered to be of child-bearing potential unless they meet one of the following criteria as documented by the Investigator:

- Post-menopausal for at least 1 year, confirmed by follicle stimulating hormone (FSH) assessment (>30 mIU/mL).
- Hysterectomy, bilateral oophorectomy or salpingectomy.
- Congenital sterility.

4.6.6 Diet

- While confined to the study center, subjects will receive standardized meals at scheduled times.
- Subjects should have a breakfast at Day 1 after the pre-dose assessment including PK blood sampling and at least 30 min before starting of IMP administration.
- Lunch at Day 1 (dosing day) will be provided at approximately 13:00 (*i.e.*, after PK blood collection of 3 hours post-dose).
- Subjects will be required to fast (except for water) at least 5 hours prior to routine safety blood sampling.
- Subjects should refrain from ingesting food or drink containing poppy seeds in the 72 hours before the Screening Visit and from 72 hours before the Check-in (Day -1).

4.6.7 Physical activity restrictions

- Must not participate in heavy physical training or excessive exercise (eg, long distance running, weight lifting or any physical activity to which the subject is not accustomed) from 7 days before first dose of IMP, during the study and until the final follow-up assessment.

4.6.8 Blood donation

- Subjects must not have donated blood more than 200 mL within 4 weeks, 400 mL within 16 weeks for female or 12 weeks for male, 600 mL within 52 weeks for female or 1000 mL within 52 weeks for male, respectively before providing a signed ICF
- Subjects must not have donated plasma or platelet component within 2 weeks before providing a signed ICF
- Subjects must agree not to donate blood for 3 months after the last follow-up assessment

5 STUDY PLAN

Study assessments are summarized in the Time and events schedule (Table 5), and the study procedures are presented in Section 6. Any deviation from study procedures should be noted in the source documents and should be reported to the Sponsor immediately.

Table 5 Time and events schedule

Study Period	Screening			Treatment Hospitalization				Follow-up
	Study Day	-21 to -2	-1	1	2	3	7 (+2)	
Informed consent		X						
Confinement				←				→
Outpatient		X						X
Inclusion/exclusion criteria		X	X					
Demography & medical history		X						
Physical examination		X	X					
Weight		X	X					
Height		X						
BMI		X	X					
Vital signs		X	X					
12-lead ECG		X	X					
Urine drugs of abuse & breath alcohol test		X	X					
Haematology, biochemistry, coagulation & urinalysis		X	X					
eGFR/eCLcr		X	X					
Hepatitis B &C and HIV		X						
Pregnancy test in female		X	X					
Protein binding blood sampling		X						
IMP administration					←			→
AE and concomitant medications								

5.1 Subject informed consent

Prior to performing any study procedures, the Investigator (or subinvestigator) will ensure that the subject is given full and adequate oral and written information about the study and the subject must sign the ICF, as described in Section 11.2.1.

5.2 Description of study phases

5.2.1 Screening period (Day -21 to Day -2)

Screening assessments will be performed from Day -21 to Day -2. There may be more than one Screening Visit.

Written informed consent will be obtained before any screening procedures are performed. The information recorded for all subjects, regardless of their suitability for the study, will be retained, and archived.

The following assessments will be performed (refer to the Time and events schedule [Table 5] for further details):

- Written informed consent
- Verify inclusion/exclusion criteria
- Medical history
- Demography
- Physical examination (including height, body weight and BMI)
- 12-lead ECG
- Vital signs (including supine blood pressure, pulse rate and infra-axillary body temperature)
- Routine laboratory evaluations (haematology; biochemistry; coagulation; urinalysis; serology[HBsAg, HCVAb, HIV antigen/antibodies]; screening for drugs of abuse and alcohol; pregnancy test and FSH for females only)
- eGFR by 3-variable Japanese equation
- eCLcr by Cockcroft-Gault formula
- AE, and prior and concomitant medication recording

Re-screening will be allowed once if the subjects will agree to perform re-screening in ICF, except for subjects who will have received the study drug. A new written informed consent will not be necessary. Re-screening will be performed within 3 months after first Screening. If re-screening will be performed within 20 days between the first screening and Day -1 (admission to the study center), only deviant parameters will be re-measured. Results of the screening assessment will be replaced with a latest assessment.

5.2.2 Treatment hospitalization period (Day -1 to Day 3)

Subjects who successfully complete screening will return to the study center in the morning of Day -1 and will remain on-site until Day 3. Inclusion and exclusion criteria will be reviewed to confirm eligibility on admission (Day -1) and Day 1 pre-dose. Eligible subjects will proceed to dosing.

5.2.2.1 Baseline phase (Day -1 to Day 1 [pre-dose])

The following procedures will be performed on Day -1 (refer to the Time and events schedule [Table 5] for further details):

- Verify inclusion/exclusion criteria

- Physical examination (including body weight and BMI)
- 12-lead ECG
- Vital signs (including supine blood pressure, pulse rate and infra-axillary body temperature)
- Routine laboratory evaluations (haematology; biochemistry; coagulation; urinalysis; screening for drugs of abuse and alcohol; pregnancy test for females only)
- eGFR and eCLcr
- Blood sampling for protein binding
- AE and concomitant medication

Re-assessment of Day -1 will be allowed once if the subjects will be agree to perform the re-assessment in ICF, except for subjects who will have re-screening or have received the study drug. A new written informed consent will not be necessary. Re-assessment will be performed within 20 days between the screening and rescheduled Day -1. Only deviant parameters will be re-measured. Results of the Day -1 assessment will be replaced with a latest assessment.

The following procedures will be performed at pre-dose on Day 1 (refer to the Time and events schedule [Table 5] for further details):

- Verify inclusion/exclusion criteria
- Physical examination
- 12-lead ECG
- Vital signs (including supine blood pressure, pulse rate and infra-axillary body temperature)
- Blood sampling for PK analysis
- AE and concomitant medication recording

5.2.2.2 Treatment phase (Day 1 to Day 3)

Only subjects meeting all the inclusion and exclusion criteria and who are suitable for the trial, will be included into the treatment phase.

A single IV infusion of 30 mg MCI-186 will be administered over 60 min on Day 1.

The following assessments will be performed during the treatment phase (refer to the Time and events schedule [Table 5] for further details):

- Physical examination (including body weight on Day 2 and Day 3)
- 12-lead ECG
- Vital signs (including supine blood pressure, pulse rate and infra-axillary body temperature)
- Routine laboratory evaluations (haematology; biochemistry; coagulation; urinalysis)
- eGFR and eCLcr
- Blood sampling for PK analysis
- AE and concomitant medication recording

5.2.3 Follow-up period (Day 7 /+2 days)

Subjects will return to the study center on Day 7 for a Follow-up Visit. The following assessments will be performed (refer to the Time and events schedule [Table 5] for further details):

- Physical examination (including body weight)
- 12-lead ECG
- Vital signs (including supine blood pressure, pulse rate and infra-axillary body temperature)
- Routine laboratory evaluations (haematology; biochemistry; coagulation; urinalysis; pregnancy test for female)
- eGFR and eCLcr
- AE and concomitant medication recording

Subjects who are withdrawn from the study should, where possible, complete the procedures scheduled for the Follow-up Visit as soon as possible after withdrawal.

5.2.4 Unscheduled visits

An unscheduled visit is defined as any visit to the study center outside of the Protocol specified time-points due to safety reasons or when a repeated measurement is required (e.g., obvious measurement errors, measuring device failure, confirmation of out-of-range results), where the subject is seen by study personnel.

6 STUDY PROCEDURES

Procedures will be performed according to the Time and events schedule (Table 5).

The time point for PK blood collection takes priority over any other scheduled study activities. Where other activities are scheduled together with PK blood collection, these will be performed before or after the blood collection and PK blood collection will be done exactly at the scheduled time point. ECG and vital signs (except body temperature) will be measured before blood collection for PK and safety assessments will be performed.

Time windows for relevant assessments will be described in a separate document.

6.1 Demography

Date of birth, sex, weight, height, race, smoking habits and alcohol consumption habits will be recorded in the CRFs.

6.2 Medical history and prior medication

Any significant and relevant past conditions and any current medical conditions prior to Screening will be recorded in the CRFs. At Screening, subjects will be asked what medications they have taken during the last 3 months. Medication taken within 30 days of Screening will be recorded as prior medication in the CRFs.

6.3 Concomitant medication

Concomitant medication is defined as any medication, other than the IMP, which is taken during the study, including prescription and over the counter medications. All concomitant medications used from the Screening visit to the last scheduled visit must be recorded in the CRFs with their daily dosage, route, duration, and reasons for administration.

6.3.1 Permitted medication

Medicines which, in the opinion of the Sponsor and Investigator, will not interfere with the study procedures or compromise safety may be used. On-demand use of acetylsalicylic acid for mild analgesia or use of oral contraceptives is permitted without discussion with the Sponsor.

In addition, any other concomitant medication may be given only if deemed necessary for the subject's welfare by the Investigator or the subject's personal physician. In subjects with renal insufficiency, the use of prescribed medications is permitted as described in Attachment 3. However, the subjects with normal renal function are restricted from use of any concomitant medications unless discussed and agreed with the Sponsor.

6.3.2 Prohibited medication

Subjects must not participate in any other clinical study involving administration of an IMP for the duration of the current study.

Subjects must not take any prescribed or non-prescribed systemic or topical medication (including herbal remedies) unless, in the opinion of the Investigator and Sponsor, the medication will not interfere with the study procedures or compromise safety.

The following medications must not be administrated from Day -1 to Day 3 (treatment hospitalization period).

- Antibiotics (Cefazolin sodium, cefotiam hydrochloride, piperacillin sodium, etc.)

- Strong sulfotransferase inducers or inhibitors (e.g., mefenamic acid, acetaminophen and ibuprofen)
- Strong UGT inducers or inhibitors (e.g., diclofenac sodium)

6.3.3 Rescue medication

There is no known antidote to MCI-186. Full resuscitation facilities will be available at all times.

6.4 Estimation of GFR (eGFR)

GFR in Groups 1 to 3 will be estimated using the 3-variable Japanese equation.

3-variable Japanese equation [7]:

$$\text{eGFR (mL/min/1.73 m}^2\text{)} = 194 \times (\text{S}_{\text{cr, std}})^{-1.094} \times (\text{Age})^{-0.287} \times (0.739 \text{ if female})$$

$\text{S}_{\text{cr, std}}$: serum creatinine measured with a standardized assay (mg/mL)

The subjects will be stratified to three different groups of renal function according to their eGFR (normal and mild or moderate impairment) at Day -1. Other eGFR measurement will be performed at 24 and 48 hr after dosing and Follow-up visit.

Table 6 Classification of Renal Function Based on Estimated GFR

Group	Description	Estimated GFR (mL/min/1.73 m ²)
1	Mild renal impairment	60 - 89
2	Moderate renal impairment	30 – 59
3	Normal renal function	≥90

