4.3 Inclusion criteria

A subject will be eligible for enrolment in the study if ALL of the following criteria apply:

All subjects

1. Male or female subjects age 20 to 75 years (both inclusive) at signature of the Informed Consent Form (ICF).
2. Able to provide written informed consent to participate in this study after reading the ICF, and after having the opportunity to discuss the study with the Investigator or designee, before any screening or study related procedures take place.
3. In the Investigator's opinion, subject is able to understand the nature of the study and any risks involved in participation, and willing to cooperate and comply with the Protocol restrictions and requirements.
4. A body weight of ≥ 45 kg in males or ≥ 40 kg in females and a body mass index (BMI) ranging from 18 to 30 kg/m^2 (inclusive) at Screening and Day -1.

5. Female subjects

- a) who are postmenopausal (absence of menses for one year or more and follicle stimulating hormone (FSH) $>30 \text{ mIU/mL}$), or
- b) who are surgically sterilised, or
- c) who are congenital sterility, or
- d) who use an effective methods of birth control from the Screening or at least 2 weeks before Investigational Medicinal Product (IMP) administration (whichever is earlier) until 14 days after the last dose of IMP.

6. Male subjects (including those who have had a vasectomy)

- a) who agree to use an adequate contraception method (e.g., condom with spermicide or partner using effective contraception) and to not donate sperm until 14 days after the last dose of IMP.

Renal impaired subjects (in addition)

7. Subjects with mild renal impairment defined as eGFR 60-89 mL/min/1.73m² and subjects with moderate renal impairment defined as eGFR 30-59 mL/min/1.73m² as determined by the 3-variable Japanese equation obtained during Screening period (i.e., within 21 days before IMP administration) and Day -1.
8. Chronic and stable renal impairment defined as no clinically significant change in disease status at least 30 days before Screening, as documented by subject's recent medical history.

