6.5 Estimation of CLcr (eCLcr)

CLcr will be estimated using Cockcroft-Gault formula.

$$\text{eCLcr (mL/min)} = \{[140 - \text{age (years)}] \times \text{weight (kg)} / 72 \times \text{S}_{\text{cr}} (\text{mg/dL})\} \times (0.85 \text{ if female})$$

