6.7.4 Routine laboratory evaluations

Blood and urine samples will be collected for routine clinical laboratory safety evaluations according to Table 5. The laboratory safety evaluations performed during the study are presented in Table 7.

Additional laboratory safety evaluations will be performed at other times, if judged to be clinically appropriate, or if the ongoing review of the data suggests a more detailed assessment of laboratory safety evaluations is required.

The Investigator will perform a clinical assessment of all laboratory safety data and the recording will be reported as 'normal', 'abnormal clinically significant (CS)', or 'abnormal not clinically significant (NCS)'. Abnormalities of clinical significance will be reported as AEs. Repeat measurements will be performed if needed.

Table 7 Routine laboratory evaluations

Haematology:	
Haemoglobin	Mean corpuscular haemoglobin (MCH)
Haematocrit	Mean corpuscular haemoglobin concentration (MCHC)
Platelet count	Mean corpuscular volume (MCV)
Red blood cell (RBC) count	White blood cell (WBC) count and differential
Biochemistry:	
Alkaline phosphatase (ALP)	Uric acid
Aspartate aminotransferase (AST)	Protein (total)
Alanine aminotransferase (ALT)	Albumin
Gamma-glutamyl transpeptidase (GGT)	Cholesterol
Potassium	Triglycerides
Sodium	High density lipoprotein-cholesterol (HDL-C)
Chloride	Low density lipoprotein-cholesterol (LDL-C)
Calcium	Lactate dehydrogenase (LDH)
Inorganic phosphate	Amylase
Glucose	Creatine kinase (CK)
Blood urea nitrogen	Creatinine ^{1,2}
Bilirubin (direct and total)	Follicle stimulating hormone (FSH) ³
Coagulation:	
Prothrombin time	Activated partial thromboplastin time (aPTT)
Urinalysis:	
Specific gravity, sediment, pH, protein, glucose, ketones, urobilinogen, bilirubin, blood hCG ⁴	
Microscopic examination ⁵	
Serology:	
Hepatitis B surface antigen (HBsAg)	Human immunodeficiency virus (HIV) antigen/antibodies
Hepatitis C virus antibody (HCVAb)	
Drugs and alcohol screen:	
Phencyclidine, cocaine, barbiturates, tetrahydrocannabinol, benzodiazepines, amphetamines/methamphetamines, opiates, and alcohol breath test	

¹ eGFR will be calculated using the 3-variable Japanese equation² eCLcr will be calculated using the Cockcroft-Gault formula³ Females only; performed at Screening only⁴ Females only; a urine pregnancy test will be performed at Screening, Day -1 and follow-up⁵ Performed only if required, based on urinalysis results

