7.3 Procedures for assigning subjects to treatment groups

The subjects will be stratified to three different groups of renal function according to their eGFR (normal and mild or moderate impairment) at Day -1. The Subject Group will be recorded in the CRFs.

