5.6 Derived variables

(1) Definition(s) of baseline(s)

The baseline of vital signs and 12-lead ECG is the final evaluable value obtained before IMP administration on Day 1.

The baseline of clinical laboratory values will be the value obtained on Day -1.

(2) Age at informed consent

Age (years) = Year of informed consent - Year of birth

Subtract 1 from the age (years) calculated above, if [Month of informed consent < Month of birth] or [Month of informed consent = Month of birth AND Day of informed consent < Day of birth].

(3) BMI

BMI = Weight [kg] / (Height [m])²

Height will be the value obtained at screening.

The value will be rounded off at the second decimal place and reported to the first decimal place.

(4) Adverse events

The MedDRA/J version 20.0 will be used as a unified dictionary in the assessment of AEs.

(5) Adverse reactions

Adverse reactions are defined as AEs that are determined to have a “Reasonable Possibility” of causal relationship to the IMP.

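### Protocol 6.4 gives creatinine in mg/mL for the eGFR equation; only mg/dL fits Table 6 and Section 6.5, and as printed the mild and moderate groups cannot be reached

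*Protocol*

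**What the plan says.** Protocol 6.4 prints the equation as 194 × Scr^-1.094 × Age^-0.287, times 0.739 for women, and defines Scr as "serum creatinine measured with a standardized assay (mg/mL"). Table 6 in the same section ("Classification of Renal Function Based on Estimated GFR") sets the bands: 60 to 89 mild, 30 to 59 moderate, 90 or above normal.

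The next section states that "CLcr will be estimated using Cockcroft-Gault formula", and that formula takes serum creatinine in mg/dL. Table 7 in Protocol 6.7.4 lists creatinine once, with two footnotes. The first reads "eGFR will be calculated using the 3-variable Japanese equation"; the second derives eCLcr from the same test.

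The equation is operative. Inclusion criterion 7 (Protocol 4.3) defines mild and moderate impairment "as determined by the 3-variable Japanese equation obtained during Screening period" and on Day -1, and criterion 10 uses it for normal function. Protocol 7.3 adds: "The subjects will be stratified to three different groups of renal function according to their eGFR".

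The SAP names the equation in 1.1 and 5.1, summarises eGFR and eCLcr at baseline in 7.2, and plots PK parameters against both in 7.8.2. SAP 5.6 gives formulas for age and BMI but not for eGFR or eCLcr. SAP 8 records no changes from the protocol.

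**The concern.** One laboratory result is given two units that differ 100-fold, and the wrong one sits beside the equation that defines the groups. Renal function group is the only factor in the ANOVA (Protocol 10.3.5.1, SAP 7.8.2), and eGFR is a horizontal axis of the exposure plots. If the unit were applied literally, every eligible subject would be classed as normal and the comparison would not exist. In the supplied text, Section 6.4 is the only place that states a creatinine unit for this equation, so anyone who looks it up finds the wrong one.

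**Working it through.** **Inputs from the documents.** The equation, its printed unit and the Table 6 bands (Protocol 6.4); ages 20 to 75, both sexes (Protocol 4.3); Cockcroft-Gault with creatinine in mg/dL (Protocol 6.5), read as (140 - age) × weight / (72 × Scr), times 0.85 for women.

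**Assumptions, for illustration only.** Creatinine of 0.8 and 1.2 mg/dL in a man aged 60; body weight 60 kg for the cross-check. The documents give no creatinine values.

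**Step 1: which creatinine values do the bands imply?** Inverting the equation:

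Scr = (194 × Age^-0.287 × [0.739 if female] / eGFR)^(1/1.094)

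| Case | Scr at eGFR 90 | Scr at eGFR 30 |
|---|---|---|
| Woman aged 75 | 0.493 | 1.346 |
| Man aged 60 | 0.689 | 1.882 |
| Man aged 20 | 0.920 | 2.510 |

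The first and last rows are the extremes over eligible ages and sexes. In mg/dL the cut-points 90 and 30 therefore span about 0.5 to 2.5 mg/dL. In mg/mL the same numbers are 49 to 251 mg/dL.

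**Step 2: which reading agrees with Section 6.5?** For a man aged 60, eGFR 60 needs Scr = 0.999. At 60 kg:

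- as mg/dL: eCLcr = 80 × 60 / (72 × 0.999) = 66.8 mL/min, in line with eGFR 60;
- as mg/mL, that is 99.9 mg/dL: eCLcr = 80 × 60 / (72 × 99.9) = 0.67 mL/min.

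Only mg/dL makes the two sections consistent, and this needs no outside source.

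**Step 3: effect of literal use.** 1 mg/dL = 0.01 mg/mL, so eGFR is multiplied by 100^1.094 = 154.17.

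| True eGFR | Value with the printed unit |
|---|---|
| 30 | 4,625 |
| 59 | 9,096 |
| 60 | 9,250 |
| 89 | 13,721 |

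For a man aged 60, 194 × 60^-0.287 = 59.9. Then:

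- 1.2 mg/dL: 59.9 × 1.2^-1.094 = 49.1 (moderate); entered as 0.012 the result is 7,566;
- 0.8 mg/dL: 59.9 × 0.8^-1.094 = 76.5 (mild); entered as 0.008 the result is 11,789.

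**Step 4: can Groups 1 and 2 be reached as printed?** From Step 1, eGFR below 90 needs creatinine above 0.493 mg/mL (49 mg/dL) in the most favourable eligible case, a woman aged 75. A man aged 60 would need more than 0.689 mg/mL (69 mg/dL). In practice the mild and moderate bands cannot be reached.

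**The case against.** The strongest reply is that this is a label error with one evident reading. The equation is named and referenced, its constants and Table 6 point to mg/dL, and so does the next section. Results in the thousands would be caught at once. The protocol also says that PK data from three mild and three normal subjects will be excluded and replaced, which suggests that mild subjects had already been classified and treated. SAP version 2.0 follows a data review meeting of 29 May 2018. All of this suggests that the printed unit was not used. It limits the practical harm, but it does not make the printed formula correct.

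On the SAP, the documents do not say that the analysis programs derive eGFR. The value may arrive with the laboratory data, and group is recorded in the CRF. The request for SAP lines is therefore a safeguard. The correction to Section 6.4 does not depend on it.

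Two reservations about the text also stand. It was extracted from PDF and the point turns on one letter, so the original page should be checked. Some SAP pages were not available, so only the supplied SAP text can be said to leave the unit uncorrected.

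**Conclusion.** The point holds. As printed, Section 6.4 conflicts with Section 6.5 and with the protocol's own bands, and literal use inflates eGFR 154-fold and puts every eligible subject at 90 or above. The factor follows from the printed exponent alone. The conclusion that mg/dL is intended rests on the printed constants, the bands and Section 6.5; the cross-check assumes a 60 kg man aged 60. The documents give no evidence that any subject was misassigned. This should be fixed because it is the rule that defines the study groups, but it does not threaten the design.

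**What to change.** - Check the unit on the original page of Protocol 6.4 and change mg/mL to mg/dL.
- Add the eGFR and eCLcr derivations, with units, to SAP 5.6, or state there that both values are supplied by the laboratory and in what unit creatinine was entered.
- Confirm that the calculation used for eligibility, group assignment and the exposure plots took creatinine in mg/dL.
- Optionally, print the Section 6.5 denominator as (72 × Scr). The supplied text can be read as multiplying by creatinine, but this may only be a fraction bar lost in extraction.

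The cost is one unit in the protocol, two lines in the SAP and one programming check.
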